## **5.4 Concomitant Medications**

All concomitant medications received within 28 days before the first dose of trial treatment and Week 12 (End of Treatment Safety Follow-up Visit) should be recorded. Anticancer therapies administered after the End of Treatment Safety Follow-up Visit will continue to be recorded until the end of study visit (Week 16).

Medications or vaccinations specifically prohibited in the exclusion criteria are not allowed during the ongoing trial. If there is a clinical indication for one of these or other medications or vaccinations specifically prohibited during the trial, discontinuation from trial therapy may be required. The investigator should discuss any questions regarding this with the Sponsor. The final decision on any supportive therapy or vaccination rests with the investigator and/or the subject's primary physician. However, the decision to continue the subject on trial therapy will rest with the Sponsor.

### **5.4.1 Acceptable Concomitant Medications**

All treatments that the investigator considers necessary for a subject's welfare may be administered at the discretion of the investigator in keeping with the community standards of medical care. All concomitant medications will be recorded on the case report form (CRF) including all prescription, over-the-counter (OTC), herbal supplements, and IV medications and fluids. Subjects may receive other medications that the investigator deems to be medically necessary unless specified in [Section 5.4.2](#) below.

### **5.4.2 Prohibited Concomitant Medications**

Subjects are prohibited from receiving the following therapies during the Screening and Treatment Phase (including retreatment for post-complete response relapse) of this trial:

- Systemic corticosteroid therapy or any other form of immunosuppressive therapy is prohibited within 7 days prior to study treatment. (Nasal or oral inhalers are permissible). Physiologic replacement doses of steroids (mineralocorticoid or less than or equal to a prednisone 10 mg daily dose) will also be permitted.

CONFIDENTIAL

This material is the property of the University of Pennsylvania. Do not disclose or use except as authorized in writing by the study sponsor.

- Anti-cancer systemic chemotherapy or biological therapy
- Immunotherapy not specified in this protocol
- Investigational agents other than pembrolizumab and itacitinib
- Radiation therapy
  - Note: Radiation therapy to a symptomatic solitary lesion or to the brain may be allowed per physician-investigator discretion, but would be regarded as a disease progression event for the primary endpoint. However as per Section 4.2.2, subjects may continue to receive pembrolizumab at the physician-investigator's discretion if the subject continues to benefit clinically from treatment.
- Live vaccines within 30 days prior to the first dose of trial treatment and while participating in the trial. Examples of live vaccines include, but are not limited to, the following: measles, mumps, rubella, chicken pox, yellow fever, rabies, BCG, and typhoid (oral) vaccine. Seasonal influenza vaccines for injection are generally killed virus vaccines and are allowed; however intranasal influenza vaccines (e.g. Flu-Mist®) are live attenuated vaccines and are not allowed.
- Glucocorticoids, in excess of physiologic doses (prednisone >10 mg per day equivalent), for any purpose other than an abbreviated course to modulate symptoms from an event of clinical interest of suspected immunologic etiology.
- CYP3A4 inhibitors and dual CYP3A4/2C9
- Fluconazole (>200mg doses)

## **5.5   Rescue Medications & Supportive Care**

### **5.5.1   Supportive Care Guidelines**

Subjects should receive appropriate supportive care measures as deemed necessary by the treating investigator. Please refer to the pembrolizumab package insert for supportive care guidelines related to pembrolizumab administration.

Toxicity management considerations for itacitinib are outlined below.

- Nausea/vomiting: Nausea and vomiting should be treated aggressively, and consideration should be given in subsequent cycles to the administration of prophylactic antiemetic therapy according to standard institutional practice. Subjects should be strongly encouraged to maintain liberal oral fluid intake.
- Anti-infectives: Subjects with a documented infectious complication should receive oral or IV antibiotics or other anti-infective agents as considered appropriate by the treating investigator for a given infectious condition, according to standard institutional practice.

## **5.6   Diet/Activity/Other Considerations**

### **5.6.1   Diet**

Subjects should maintain a normal diet unless modifications are required to manage an AE such as diarrhea, nausea or vomiting.

CONFIDENTIAL

This material is the property of the University of Pennsylvania. Do not disclose or use except as authorized in writing by the study sponsor.

### **5.6.2 Contraception**

Pembrolizumab and/or itacitinib may have adverse effects on a fetus in utero. Furthermore, it is not known if pembrolizumab and/or itacitinib have transient adverse effects on the composition of sperm. Therefore while enrolled, all subjects must agree not to participate in a conception process (i.e. active attempt to become pregnant or to impregnate, sperm donation, in vitro fertilization, etc).

Female subjects of reproductive potential (women who have reached menarche or women who have not been post-menopausal for at least 24 consecutive months, i.e., who have had menses within the preceding 24 months, or have not undergone a sterilization procedure [hysterectomy or bilateral oophorectomy]) must have a negative serum or urine pregnancy test performed within 72 hours of Cycle 1/Day 1 as per the Trial Flow Chart.

All participants participating in sexual activity that could lead to pregnancy must agree to use two methods of birth control. The two birth control methods can be either two barrier methods or a barrier method plus a hormonal method to prevent pregnancy. Subjects should start using birth control from screening throughout the study period up to 120 days after the last dose of study therapy.

The following are considered adequate barrier methods of contraception: diaphragm, condom (by the partner), copper intrauterine device, sponge, or spermicide. Appropriate hormonal contraceptives will include any registered and marketed contraceptive agent that contains an estrogen and/or a progestational agent (including oral, subcutaneous, intrauterine, or intramuscular agents). Male sterilization (i.e. vasectomy) is also considered an acceptable method of birth control as long as a barrier method is also utilized.

Subjects should be informed that taking the study medication may involve unknown risks to the fetus (unborn baby) if pregnancy were to occur during the study. In order to participate in the study they must adhere to the contraception requirement above. If there is any question that a subject will not reliably comply with the requirements for contraception, that subject should not be entered into the study.

### **5.6.3 Use in Nursing Women**

It is unknown whether the study drugs are excreted in human milk. Since many drugs are excreted in human milk, and because of the potential for serious adverse reactions in the nursing infant, subjects who are breast-feeding are not eligible for enrollment.

## **5.7 Subject Withdrawal/Discontinuation**

A subject may be prematurely discontinued from study treatment for any of the following reasons:

- Withdrawal of consent
- Confirmed radiographic disease progression per RECIST 1.1; (as per standard of care, a patient receiving pembrolizumab who experiences asymptomatic progression of disease may be continued on therapy until progression is confirmed with a subsequent scan).
- Unacceptable adverse experiences or toxicities (see [Section 5.3.1.2](#))
- Intercurrent illness that prevents further administration of treatment

CONFIDENTIAL

This material is the property of the University of Pennsylvania. Do not disclose or use except as authorized in writing by the study sponsor.

- Investigator's decision to withdraw the subject
- Confirmed positive serum pregnancy test
- Noncompliance with trial treatment or procedure requirements
- Institution of alternative systemic treatment
- Other Administrative reasons

Subjects who discontinue from study treatment will complete and End of Study Visit per the Trial Flow Chart in [Section 6.0](#).

## **5.8 Subject Replacement Strategy**

Subjects who either experience documented progressive disease during the first 12 weeks of treatment or complete the first 12 weeks of treatment and undergo re-staging are considered evaluable and will not be replaced. Subjects who complete study treatments but are unable to complete planned biopsies will also be considered evaluable for response and adverse events. All other subjects will be considered non-evaluable and will be replaced.

## **5.9 Clinical Criteria for Early Trial Termination**

The 3-stage optimal design tests the null hypothesis that the ORR  $\leq 35\%$  (clearly inferior to pembrolizumab) versus the alternative that the ORR  $\geq 55\%$  (clearly superior to pembrolizumab) [2]. ORR will include both subjects with partial responses and complete responses, per RECIST 1.1. Stable disease will not be considered a response. Eleven evaluable subjects will be entered into the first stage of the study. If 2 or fewer of these 11 subjects respond, then the trial will be terminated. If at least 3 of these subjects respond, then an additional 19 evaluable subjects will be entered into the second stage of the study. If 12 or fewer of these 30 subjects respond, then the trial will be terminated. If at least 13 of these subjects respond, then an additional 18 evaluable subjects will be entered into the third stage of the study. If 20 or fewer of these 48 subjects respond, then it will be concluded that the regimen does not merit further investigation. If at least 21 of these 48 subjects respond, then it will be concluded that the regimen merits further investigation. If the true objective response rate is 35%, then the probability of recommending the regimen for further investigation (false positive error), is 0.100. While if the true objective response rate is 55%, then the probability of recommending the regimen for further investigation (power), is 0.906. If the true objective response rate is 35%, then the probability of early termination of the trial by the end of the second stage is 0.786. The software program, PASS v14 was employed to define this 3-stage design.

A Bayesian termination rule for unacceptable toxicity (defined in [Section 8.1](#)) will be employed to monitor safety. Assuming a minimally informative beta (1,5) prior, which is information equivalent to 1 of 6 treated subjects with unacceptable toxicity. If the number of subjects with unacceptable toxicity in the first stage of 2-stage design is:  $\geq 2$  in first 3 subjects,  $\geq 3$  in first 6,  $\geq 4$  in first 9, or in the second stage of the design is:  $\geq 5$  in first 12,  $\geq 6$  in first 15,  $\geq 7$  in first 18,  $\geq 9$  in first 25 subjects,  $\geq 10$  in first 30 or in the third stage of the design is:  $\geq 12$  in first 35,  $\geq 13$  in first 40 and  $\geq 14$  in first 45, then termination will be considered as it is likely that the rate of unacceptable toxicity is  $>25\%$ .

### **5.10 *Clinical Criteria for Early Trial Termination due to Trial Conduct or Other Factors***

Early trial termination will occur for any of the following:

1. Incidence or severity of adverse drug reaction in this or other studies indicates a potential health hazard to subjects
2. Plans to modify or discontinue the development of the study drug

CONFIDENTIAL

This material is the property of the University of Pennsylvania. Do not disclose or use except as authorized in writing by the study sponsor.

## 6.0 TRIAL FLOW CHART

### 6.1 Study Flow Chart

Trial Period:	Treatment Cycles (q3 weeks)					End of Study Treatment 	End of Study 
Treatment Cycle/Title:	Screening Visit	Cycle1	Cycle 2	Cycle 3	Cycle 4	EOT Safety Follow-up Visit	
Scheduling Window (Days):	-28 to -1	Wk1	Wk 3 (± 3)	Wk 6 (± 3)	Wk 9 (± 3)	Week 12 (±5)	Week 16(±10)
Informed Consent	X						
Inclusion/Exclusion Criteria Assessment	X						
Demographics and Medical History	X						
Prior and Concomitant Medication Review	X	X-----X				X	
Pembrolizumab Administration		X	X	X	X		
Itacitinib Administration				X	X		
Post-study anticancer therapy status						X	X
Adverse Event Assessment	X	X-----X				X	X
Full Physical Examination	X				X	X	
Directed Physical Examination 		X	X	X			X
Vital Signs and Weight	X	X	X	X	X	X	
ECOG Performance Status	X	X	X	X	X	X	
Pregnancy Test – Urine or Serum β-HCG 	X	X 					
PT/INR and aPTT	X 						
CBC with Differential 	X 		X	X	X	X	X
Comprehensive Serum Chemistry Panel 	X 		X	X	X	X	X

CONFIDENTIAL

This material is the property of the University of Pennsylvania. Do not disclose or use except as authorized in writing by the study sponsor.

Trial Period:	Treatment Cycles (q3 weeks)					End of Study Treatment 	End of Study 
	Screening Visit	Cycle 1	Cycle 2	Cycle 3	Cycle 4		
Treatment Cycle/Title:	-28 to -1	Wk1	Wk 3 (± 3)	Wk 6 (± 3)	Wk 9 (± 3)	Week 12 (±5)	Week 16(±10)
TSH 	X 		X			X	
Tumor Imaging 	X 		X 		X 		
Tumor Biopsies 			X 		X 		
Archived Tumor Tissue Sample Collection	X 						
Research Blood Collection 	X	X	X	X	X	X	

1. The order of preference for biopsy site, if safely accessible, is primary tumor > solid organ metastasis (including thoracentesis) > lymph node metastasis. Preference will be made to biopsy the same site for both biopsies, if safe and feasible.
2. Up to 78mL of blood will be collected for research studies. Please refer to the Study Laboratory Manual for additional details related to sample collection and handling.
3. Female subjects of reproductive potential only. A negative pregnancy test is required within 72 hours of Cycle 1/Day 1.
4. Directed physical examinations will be symptom and disease driven based on physician discretion.
5. RECIST 1.1 will be used in this study for assessment of tumor response. While either CT or MRI may be utilized, as per RECIST 1.1, CT is the preferred imaging technique in this study. Tumor imaging timing should follow calendar days and should not be adjusted for delays in cycle starts or extension of pembrolizumab cycle duration.
6. The End of Treatment (EOT) Safety Follow-up Visit will occur at Week 12 (+/-5d). The End of Study (EOS) Visit will occur at Week 16 (+/-10d). If the PI considers it beneficial for the subject, a fifth cycle may be administered prior to EOS visit. Subjects who remained on study treatment beyond Week 16 prior to the approval of Protocol Amendment V5, will be asked to undergo an End of Study Visit at their next clinic appointment prior to being withdrawn from the study. Please refer to **Section 7.1.6.1** for how to handle subjects who prematurely discontinue from study treatment.
7. Baseline tumor imaging to be performed within 30 days prior to Cycle 1/Day 1. A PET/CT may be used to fulfill baseline imaging requirements, however a PET/CT cannot be substituted for post-infusion imaging. Please refer to **Section 7.1.2.6** for additional information.

CONFIDENTIAL

This material is the property of the University of Pennsylvania. Do not disclose or use except as authorized in writing by the study sponsor.

8. Please refer to **Table 4** for additional information. After Cycle 1, pre-dose laboratory procedures can be conducted up to 72 hours prior to dosing. Results must be reviewed by the investigator or qualified designee and found to be acceptable prior to each dose of trial treatment.
9. Screening laboratory tests are to be performed within 10 days prior to Cycle 1/Day 1.
10. Performed 7-14 days after Cycle 2 of pembrolizumab. Tumor imaging will be used for biopsy planning only, and no treatment decisions will be made based upon the results.
11. Performed at the end of Cycle 4, before the end of study visit. Imaging performed at this timepoint will be used to evaluate objective response by RECIST 1.1.
12. An archived tumor tissue sample may be collected for exploratory analysis if available. Subjects will not undergo an additional procedure to obtain this sample. Please refer to the Lab Manual for additional instructions.

CONFIDENTIAL

This material is the property of the University of Pennsylvania. Do not disclose or use except as authorized in writing by the study sponsor.

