13. Pregnant or breastfeeding women
14. Prior therapy with an anti-PD-1, anti-PD-L1, anti-PD-L2, anti-CD137, or anti-Cytotoxic T-lymphocyte-associated antigen-4 (CTLA-4).
15. Known history of Human Immunodeficiency Virus (HIV) (HIV 1/2 antibodies).
16. Known active Hepatitis B (e.g., HBsAg positive or HBV DNA detectable) or Hepatitis C (e.g., HCV RNA [qualitative] is detected).
17. Anticipated receipt of any live vaccine within 30 days prior to the first dose of trial treatment.

Note: For the purposes of determining eligibility above, enrollment is defined as the date of subject consent.

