## 7.0 TRIAL PROCEDURES

### 7.1 *Trial Procedures*

The Trial Flow Chart - **Section 6.0** summarizes the trial procedures to be performed at each visit. Individual trial procedures are described in detail below. It may be necessary to perform these procedures at unscheduled time points if deemed clinically necessary by the investigator.

Furthermore, additional evaluations/testing may be deemed necessary by the Sponsor for reasons related to subject safety. In these cases, such evaluations/testing will be performed in accordance with those regulations.

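### Cheap safety improvement: repeat the pregnancy test before itacitinib starts at Cycle 3/Day 1, when the last required negative result is nominally 42–45 days old

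*Combined protocol and SAP*

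**What the plan says.** All references are to the combined protocol and SAP.

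- **Testing schedule.** In section 6.1 the Pregnancy Test row is marked at Screening and Cycle 1 and is blank from Cycle 2 to End of Study. Footnote 3 limits it to women of reproductive potential and adds: "A negative pregnancy test is required within 72 hours of Cycle 1/Day 1". Section 5.6.2 says the same in prose: such women "must have a negative serum or urine pregnancy test performed within 72 hours of Cycle 1/Day 1 as per the Trial Flow Chart". Table 4 lists the urine and serum assays but sets no dates for them.
- **Drug schedule.** Pembrolizumab is given from Cycle 1. Itacitinib starts at Cycle 3/Day 1 and runs daily for up to 42 days (section 5.3.2).
- **Hazard.** Section 5.6.2 names both drugs together: "Pembrolizumab and/or itacitinib may have adverse effects on a fetus in utero".
- **Prevention.** Section 5.1.2 excludes "Pregnant or breastfeeding women". Section 5.6.2 adds three safeguards: "all subjects must agree not to participate in a conception process"; "All participants participating in sexual activity that could lead to pregnancy must agree to use two methods of birth control"; and "If there is any question that a subject will not reliably comply with the requirements for contraception, that subject should not be entered".
- **Discretionary testing.** Section 7.1 says of the trial procedures: "It may be necessary to perform these procedures at unscheduled time points if deemed clinically necessary by the investigator". It also lets the Sponsor ask for further tests on safety grounds.
- **Once a pregnancy is known.** Sections 4.2.2 and 5.7 make it a reason to stop treatment, and section 10.3.2 requires a report to the sponsor within 24 hours.

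**The concern.** The protocol asks for a fresh negative result, no more than three days old, before the first drug. It asks for nothing comparable six weeks later, when an investigational drug is added. Section 5.7 makes a confirmed positive serum test a reason to stop, but no scheduled on-treatment test would produce one.

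If contraception fails during Cycles 1–2 and nothing prompts an unscheduled test, a woman could begin itacitinib, and go on receiving pembrolizumab, while unknowingly pregnant. Early signs are easy to misattribute: section 4.2.2 lists nausea among the most frequent events reported with this combination.

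What is at stake is maternal and fetal safety alone. The response rate, the stopping boundaries and the error rates of the three-stage design are unaffected.

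**Working it through.** The check is calendar arithmetic on the age of the last required negative result.

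**Inputs**
- Cycle length 21 days (section 1.0). Call Cycle 1/Day 1 day 0.
- Cycle 1 test taken t = 0 to 3 days before day 0 (footnote 3; section 5.3.2 places procedures before dosing).
- Visit window ±3 days (sections 5.3.2 and 6.1).
- 42 daily itacitinib doses, so the 42nd falls 41 days after Cycle 3/Day 1.

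**Reproducing the plan's own timing.** Cycle 3/Day 1 = 2 × 21 = day 42, which is the flow chart's Week 6. Cycle 4/Day 1 = 3 × 21 = day 63.

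**Current plan.** Age = (day of dose) + t.
- First itacitinib dose, nominal: 42 + 0 = 42 to 42 + 3 = 45 days.
- With ±3 days around Week 6: (42 − 3) + 0 = 39 to (42 + 3) + 3 = 48 days.
- If the Cycle 2 and Cycle 3 windows accumulate: (42 − 6) + 0 = 36 to (42 + 6) + 3 = 51 days.
- 42nd dose, day 42 + 41 = 83: 83 to 86 days nominal, 80 to 89 with the ±3-day window.

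**Toxicity delay.** Section 5.3.2 allows longer pembrolizumab intervals but gives no length. Assuming Cycle 3 slips by 7 days, the age at first itacitinib dose is 49–52 days (46–55 with the window). Assuming 21 days, it is 63–66 days (60–69 with the window).

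**With a Cycle 3 test, 0–3 days before dosing**
- First itacitinib dose: 0–3 days.
- 42nd dose: 41 + 0 = 41 to 41 + 3 = 44 days.

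**With Cycle 3 and Cycle 4 tests**
- Dose 21 (day 62) rests on the Cycle 3 result: 20 + 0 = 20 to 20 + 3 = 23 days.
- Dose 42 (day 83) rests on the Cycle 4 result: 83 − 63 = 20, so again 20 to 23 days.
- The maximum at any scheduled itacitinib dose is 23 days. With ±3 days on both visits, the gap can shift by 6 days: 20 + 6 + 3 = 29 days.

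These are ages of a test result, not probabilities of pregnancy.

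**The case against.** The strongest reply is that this is a design preference. No requirement is breached, and the protocol relies on layered prevention: exclusion at entry, two contraceptive methods from screening to 120 days after the last dose, a broad definition of reproductive potential, questioning about adverse events at every contact, and freedom to test at any time. The group may also be tiny. The maximum enrolment is 50 (section 8.3). If 2–10% were women of reproductive potential, an assumed figure, that would be 1 to 5 women. All of this stands as to weight. It does not supply detection: the preventive rules can fail, and discretionary testing needs a prompt.

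A second objection is that singling out Cycle 3 is arbitrary. On the same logic, pembrolizumab at Cycle 2/Day 1 rests on a result 21 to 24 days old (21 + 0 to 21 + 3). A reader might infer that itacitinib is the greater fetal hazard. The documents do not support that: section 5.6.2 treats the drugs alike, and itacitinib's toxicities are left to the Investigator's Brochure (section 9.1.5). Cycle 3 is chosen only because a second, investigational drug begins there.

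A reader might also infer that a Cycle 3 test would prevent exposure. It would not do so fully. A very recent conception can be missed, a later one needs a later test, and pembrolizumab exposure in Cycles 1–2 has already happened.

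Finally, the text already reflects Amendment V5. The change would reach only women not yet at Cycle 3 (or Cycle 4 for the repeat), and the documents do not say how many remain.

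**Conclusion.** The point holds as a low-cost safety improvement, with high confidence in the text and the arithmetic. The gap is an unscheduled check: the protocol is internally consistent on this matter and nothing in it is contradicted.

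A Cycle 3 test would bring the age of the required result at the first itacitinib dose from a nominal 42–45 days down to 0–3 days. Adding Cycle 4 would cap it at 23 days for any scheduled itacitinib dose (29 with windows). The figures assume that the Cycle 1 test precedes dosing by at most 72 hours and, unless stated otherwise, that cycles run on time.

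The absolute benefit cannot be computed, because neither the number of women of reproductive potential nor any pregnancy rate is given. It would be wrong to read the finding as evidence that exposure is likely, or as a flaw in the trial's main inference.

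**What to change.** 1. **Section 6.1:** mark the Pregnancy Test row at Cycle 3, and preferably also at Cycle 4.
2. **Footnote 3 and the testing sentence in section 5.6.2:** after the Cycle 1/Day 1 requirement add *and again within 72 hours before the first itacitinib dose (Cycle 3/Day 1)*, and preferably *and Cycle 4/Day 1*.
3. **Assay:** urine or serum, as now allowed. Serum can be run on the pre-dose CBC and chemistry blood already scheduled at both cycles. Footnote 8 lets those samples be taken up to 72 hours before dosing and requires review before each dose. Table 4 already sends an unclear urine result to a serum test, and section 5.7 needs no edit.

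The Cycle 4 repeat is recommended because the Cycle 3 result alone would be 41–44 days old at the last itacitinib dose.

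**Cost.** One assay per woman of reproductive potential (two with Cycle 4), with no new visit or needle stick; a minor amendment with IRB approval (section 13.0); and now and then a brief dose hold while an unclear result is settled. Whether the consent form must also change cannot be told from these documents.
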